## Secondary Analyses:

A secondary hypothesis is that individuals receiving anti-SARS-CoV-2 convalescent plasma are likely to have less disease severity than control. We have devised a clinical event scale for disease severity based on the COVID clinical severity scale which is composed of clinical events that range from being not infected to death. The event scale is as follows:

1. Death
2. Requiring mechanical ventilation and/or in ICU
3. non-ICU hospitalization, requiring supplemental oxygen;
4. non-ICU hospitalization, not requiring supplemental oxygen  
or  
a stay of >24 hours for observation in an ED, field hospital, or other healthcare unit\*  
or  
any receipt of O2 for >24 hours, outside of hospital\*
5. Not hospitalized, but with clinical and laboratory evidence of COVID-19 infection (symptomatic infection)

---

 Positive molecular testing for SARS-CoV-2

\*with surge of infections in December 2020 and hospitals becoming more full, these two were put into the clinical events scale as hospitalization equivalents

6. Not hospitalized, no clinical symptoms compatible with COVID-19, but with laboratory evidence of COVID-19 infection (asymptomatic infection)
7. No symptoms compatible with infection, no laboratory evidence of COVID-19 (No indication of infection)

This analysis will be done using the status of participants by day 32 (corresponding to day 28 visit allowing for window around the scheduled visit) using a doubly robust estimators for ordinal outcomes and adjusted for the pre-specified candidate variables selected via the algorithm as described above. The doubly robust estimator that will be used is that as outlined by Benkeser et al. (2020) based upon a non-parametric extension of the log-odds ratio by Diaz et al. (2016). A sensitivity analysis will be done in which participants who have indication of positive infection (e.g. clinical scale event <7) at  $\leq 3$  days after transfusion.

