**Convalescent Plasma to Stem Coronavirus: A Randomized
Controlled Double Blinded Phase 2 Study Comparing the
Efficacy and Safety of Human Coronavirus Immune Plasma
(HCIP) vs. Control (SARS-CoV-2 non-immune plasma) among
Adults Exposed to COVID-19**

NCT 04323800

Protocol

Version December 23, 2020

1. PROTOCOL SUMMARY:

Long title: Convalescent Plasma to Stem Coronavirus: A Randomized Controlled Double Blinded Phase 2 Study Comparing the Efficacy and Safety of Human Coronavirus Immune Plasma (HCIP) vs. control (SARS-CoV-2 non-immune plasma) among Adults Exposed to COVID-19

Short title: CSSC-001

Clinical Phase: 2

IND Sponsor: Johns Hopkins University

Conducted by: Johns Hopkins University as lead institution for a consortium of sites

Sample Size: 500

Study Population: High-risk subjects aged 18 years of age and older who have experienced a close contact exposure to a person with COVID-19 in the past 120 hours AND have not yet themselves developed symptoms of COVID-19

Study Duration: April 1, 2020 to December 31, 2022

Study Design: This randomized, controlled, double-blinded phase 2 trial will assess the efficacy and safety of Anti- SARS-CoV-2 convalescent plasma as prophylaxis following exposure to COVID-19 (as defined in the inclusion criteria). Adults 18 years of age and older with high risk exposure as defined by CDC may participate. A total of 500 eligible subjects will be randomized in a 1:1 ratio to receive either high titer anti-SARS-CoV-2 plasma or control (SARS-CoV-2 non-immune plasma).

The following will be assessed in all subjects:

- Safety and efficacy: Day 0 (baseline), 1, 3, 7, 14, 28, 60 and 90. May be performed by telemedicine on days when laboratory testing not scheduled.
- Blood antibody titer¹ to SARS-CoV-2s: Day -1 to 0, 1, 7, 14 and 90
- SARS-CoV-2 molecular testing from nasopharyngeal swab, throat samples: Day -1 to 0, 1,7, 14 and 28 and at any time when there is clinical suspicion for COVID-19

Study Agent:

- SARS-CoV-2 convalescent plasma (1 unit; minimum of 175 mL collected by pheresis from a volunteer who recovered from COVID-19 disease and has SARS-CoV-2 antibody titers \geq 1:320
- Control plasma: Plasma collected from a volunteer donor prior to January 1, 2020 will not be tested for SARS-CoV-2 antibodies. Plasma collected after December 31, 2019 will be confirmed as SARS-CoV-2 seronegative.

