## Study Design

CSSC-001 is a two-arm, parallel-group, multi-center, randomized superiority trial in which outpatient adults with recent exposure to SARS-CoV-2 but no current infection will be randomized to receive either human coronavirus immune plasma (HCIP) or control (SARS-CoV-2 non-immune) plasma. This randomized, double-blind, controlled, phase 2 trial will assess the efficacy and safety of HCIP to reduce the cumulative incidence of the development of COVID-19 during study follow-up. Adults 18 years of age or older, with high risk exposure (see below for definition) to person with COVID-19 within 96 hours of enrollment (and 120 hours of receipt of plasma). A total of approximately 500 eligible subjects will be randomized in a 1:1 ratio to either HCIP or control plasma.

**High risk exposure will be defined** as currently defined by CDC and modified as the CDC makes changes. Currently this includes any close contact exposure (as defined by CDC guidelines) to person with COVID-19. Health Care Personnel (HCP) are defined as physicians, nurses, nursing assistants, therapists, technicians, emergency medical service personnel, dental personnel, pharmacists, laboratory personnel, autopsy

personnel, students, trainees and contractual staff. Persons not directly involved in patient care such as clerical, dietary, housekeeping, laundry, security, maintenance, billing, and volunteers, but who are potentially exposed to SARS-CoV-2 in the healthcare setting, also fall under the category of HCP in this protocol.

*Primary Outcome:*

- The primary outcome of CSSC-001 will be the cumulative incidence by day 28 of the development of COVID-19 (symptoms compatible with infection and/or RT-PCR positive) regardless of disease severity comparing those randomized to HCIP to those who are transfused with control plasma.

*Secondary Outcome:*

- Compare the cumulative incidence of disease severity between those randomized to HCIP and control plasma. Severity of disease will be measured using a clinical event scale of disease severity evaluated up to Day 28:
  1. Death
  2. Requiring mechanical ventilation and/or in ICU
  3. non-ICU hospitalization, requiring supplemental oxygen;
  4. non-ICU hospitalization, not requiring supplemental oxygen, or a stay of >24 hours for observation in an ED, field hospital, or other healthcare unit\*, or any receipt of O2 for >24 hours, outside of hospital\*

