- The data system will automatically store the date and time of assignment, the identity of the clinical site personnel making the assignment, the participant's ID, and the treatment group assignment.

The data system will provide access to randomization materials, including a visit schedule and allowable time windows for visits.

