Analyses will be done to explore differences in the outcomes between the treatment groups. Results of these analyses will be presented unadjusted (crude) and adjusted for covariates. Variables chosen for adjustment are specifically for increasing precision in estimates of treatment efficacy and thus must be predictive of disease outcome [Diaz et al, Lifetime Data Anal (2019): 25]. To identify the adjustment variables, we will utilize a hybrid approach of pre-specifying some variables and using an algorithmic approach to identify variables to adjust for among pre-specified candidate variables. Variables that we are near certain to be predictive of outcome will be adjusted for. Age has been consistently related to worse outcomes for COVID-19 and therefore will be included in analyses for adjustment. Other pre-specified variables that will be candidates for inclusion in primary analysis will be determined via an algorithmic approach and these variables will include: clinical site, race, ethnicity, sex, category of exposure, hematology factors and other laboratory markers (i.e., CBC and metabolic panels), body mass index, ABO blood group, prescription steroid, targeted physical exam, and prior comorbidities that have specifically been associated with worse COVID-19 outcomes including: asthma, chronic kidney disease, chronic lung disease (COPD, idiopathic pulmonary fibrosis, cystic fibrosis), diabetes, hemoglobin disorders (thalassemia, sickle cell disease), immunocompromising conditions (cancer, HIV, organ transplantation, prolonged use of corticosteroids), chronic liver disease, hypertension, and serious heart conditions (heart failure, coronary artery disease, cardiomyopathies, pulmonary hypertension), obesity, smoking status, dementia, down syndrome, pregnancy, stroke/cerebrovascular disease, and substance use disorders [updated to CDC list on website on 5/29/2021 and Guan et al Eur Respir J. 2020 May; 55(5)]. To determine which of these pre-specified candidate variables to be included, we will conduct variable selection by random survival forest in the entire sample (i.e., not including an indicator term for treatment arm) and blinded to treatment allocation. The variable importance and 95% confidence intervals [Ishwaran et al Statistics in Medicine. 2019;38] shall be used to identify predictive variables for the outcome and included in analytical models. Specifically, variables in which the 95% CI for the variable importance from the random forest does not contain 0 will be adjusted for. This should reduce the number of variables that the analysis adjusts for in order to minimize the degrees of freedom that are used while allowing the analysis to include the variables that have the most correlation with the outcome in order to maximize precision. This hybrid approach will be done on the full sample (i.e., modified ITT sample) and not include the treatment arm (i.e., among entire sample without controlling for convalescent or control plasma) in order to identify the prognostic baseline variables for entire sample.

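### Calendar period of randomization is missing from the covariates chosen for precision, although the date is stored for every participant

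*SAP*

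**What the plan says.** **Covariates.** The SAP (Statistical Principles) adjusts in order to increase precision. One variable is forced in: "Age has been consistently related to worse outcomes for COVID-19 and therefore will be included in analyses for adjustment". The rest are candidates kept only if the 95% interval for their random-forest importance excludes 0: "these variables will include: clinical site, race, ethnicity, sex, category of exposure, hematology factors and other laboratory markers", followed by BMI, blood group, steroid use and a long list of comorbidities. No calendar variable appears there or in the shorter list in Protocol 5.2. The ordinal severity analysis is "adjusted for the pre-specified candidate variables selected via the algorithm as described above", so it has none either. None of the sensitivity analyses in the SAP concerns calendar time.

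**Why time could matter.** The Protocol summary gives "Study Duration: April 1, 2020 to December 31, 2022". The SAP (Study Design) defines high-risk exposure "as currently defined by CDC and modified as the CDC makes changes", so the eligible population can drift. The SAP (Power and Sample Size) allows control risk anywhere from 0.10 to 0.20, and its stopping guidelines mention the course of the pandemic and secondary outbreaks.

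**The date is available.** SAP, Randomization: "The data system will automatically store the date and time of assignment".

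**Severity scale.** The SAP places observation stays over 24 hours and out-of-hospital oxygen over 24 hours at level 4 of a seven-level scale, with the footnote "with surge of infections in December 2020 and hospitals becoming more full, these two were put into the clinical events scale as hospitalization equivalents".

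**The concern.** The stated purpose of adjustment is precision, and the list runs to dozens of candidates. It nevertheless omits a baseline variable that is plausibly prognostic for infection after exposure, is known for everyone and costs nothing to collect. If attack rates move over the study, the variation between eras stays in the error term of the primary risk difference, except for what site or exposure category happens to absorb. At stake is a slightly wider standard error than necessary.

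A second, smaller matter is the coding of the two added severity events in participants followed before December 2020. No rule is stated, and the scale appears in more than one form.

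**Working it through.** **1. The plan's own sample size.** Inputs (Protocol 5.1; SAP, Power and Sample Size): risks 0.13 and 0.065, 80% power, one-sided alpha 0.05. Under an exponential model the hazard ratio is ln(0.935)/ln(0.87) = 0.4826. Schoenfeld events are 4(1.645 + 0.842)²/(ln 0.4826)² ≈ 46.6. Divided by the mean event probability 0.0975, this gives 478, which is 2.1% below the stated 488. At the final-analysis threshold of 0.047 the result is 489. The stated figure reproduces and is not in dispute.

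**2. Value of an era term.** Assumptions: two eras, mean control risk 0.13, risk ratio 0.5 in each era, 250 per arm, one-sided 0.047.

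- Variance without an era term (per-arm n factored out): 0.13×0.87 + 0.065×0.935 = 0.1131 + 0.0608 = 0.1739.
- With equal eras whose control risks are 0.13 ± d, the variance removed is d² + (d/2)² = 1.25d².
- Threefold case: risks 0.065 and 0.195, d = 0.065. Removed: 1.25×0.004225 = 0.00528. Reduction: 0.00528/0.1739 = 3.0%.
- Power = Φ(0.065/√(V/250) − 1.675). With V = 0.1739 this is 0.785. With V = 0.1739 − 0.0053 = 0.1686 it is 0.796.

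| Control-risk ratio between equal eras | Control risks | Variance cut | Power | Equivalent N |
|---|---|---|---|---|
| no era term | 0.13 | – | 0.785 | 500 |
| 1.5 | 0.104 / 0.156 | 0.5% | 0.787 | 498 |
| 2 | 0.087 / 0.173 | 1.4% | 0.790 | 493 |
| 3 | 0.065 / 0.195 | 3.0% | 0.796 | 485 |
| 4 | 0.052 / 0.208 | 4.4% | 0.801 | 478 |
| 6 | 0.037 / 0.223 | 6.2% | 0.808 | 469 |

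With 30% of participants in the low-risk era and 70% in the high-risk era, the 1.5- to 3-fold range gives 0.35% to 1.8%, and sixfold gives 3.2%.

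As a cross-check on the SAP's own range, let the two equal eras have control risks 0.10 and 0.20. Then (0.05² + 0.025²)/(0.15×0.85 + 0.075×0.925) = 0.003125/0.1969 = 1.6%.

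The baseline of 0.785 falls below the planned 80% because this is an unadjusted risk-difference test at 0.047. Only the change between rows matters.

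**3. Severity scale, place by place.**

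| Place | The two events |
|---|---|
| Protocol summary | separate levels 5 and 6 of seven |
| Protocol 4.1.3 and 6.1 | absent; five levels |
| SAP, Study Design and Secondary Analyses | merged into level 4 of seven |

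To size the coding question, take an illustrative control distribution over levels 1 to 7 of 0.001, 0.003, 0.004, 0.007, 0.115, 0.05 and 0.82, with the first six halved in the treated arm. The average log-odds ratio over the six cut-points is −0.7249. Moving 0.5% to 2% of controls, and half that share of treated participants, from level 5 to level 4 gives −0.7253 to −0.7266. At 250 per arm that is about 2 to 8 participants, out of about 49 symptomatic cases expected (250×0.13 + 250×0.065 = 48.75).

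**The case against.** The strongest reply is that the gain is tiny and the plan is already close to sufficient. Site and exposure category are candidates and may absorb part of any era effect. The SAP (Randomization) also allows regression adjustment for baseline imbalance if needed, and site-stratified permuted blocks roughly balance the arms over time. Leaving the term out is, if anything, slightly conservative. All of this stands and caps the size of the point. It does not remove it: the imbalance clause is generic and names no calendar variable, and the candidate list exists to catch such precision gains.

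A reader might infer three stronger things, none of which the documents support.

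- **That the same event is scored differently by era.** The SAP states one seven-level scale for the whole analysis. Its footnote explains why two events were added; it sets no start date and does not say that earlier participants keep an older scale. The SAP also cites a CDC list as of May 2021, so this text postdates the addition and can naturally be read as covering everyone. What is missing is a stated coding rule.
- **That the primary result is affected by the scale or by the CDC clause.** The SAP's working primary endpoint is a positive molecular test, which does not use the scale. The CDC clause governs who is eligible and scores no outcome.
- **That the gain is larger.** Control-arm variance alone gives 0.065²/0.1131 = 3.7% in the threefold case, but the risk difference carries both arms and the figure is 3.0%. Likewise, April to mid-December 2020 is about 26% of the planned calendar (8.5 of 33 months), but that is not a share of participants; accrual by date is not given.

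**Conclusion.** The covariate point holds as a minor, cost-free improvement. Omitting calendar period costs about 0.5% to 3% of the variance of the risk difference for 1.5- to 3-fold differences in control risk between equal eras. That is 0.2 to 1.1 points of power, or the equivalent of 2 to 15 participants out of 500. There is no bias between arms.

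These sizes rest on assumed era-specific risks, a constant risk ratio of 0.5 and the planning rates, which the documents give for symptomatic disease although the SAP's primary endpoint also counts asymptomatic infection. They are closer to upper limits for each scenario, because site or exposure category may capture some of the effect and the forest may not select the term.

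The severity-scale point is a request for clarification only. Back-coding is unspecified, and the scale versions conflict. In the illustration the effect on the ordinal summary is negligible. The separate cumulative incidence of each clinical event in Protocol 5.2.2 would depend on the coding rule more directly, but that too is secondary.

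**What to change.** 1. In the SAP (Statistical Principles), add calendar period of randomization, for example calendar quarter, to the candidate covariates for the primary and ordinal analyses. Selection stays blinded to arm and uses a stored baseline date, so the cost is one line of SAP text and no new data.
2. State in the SAP (Secondary Analyses) whether the final scale applies to all participants, with earlier observation stays and out-of-hospital oxygen coded from medical records, or say that the records do not allow it. The cost is a sentence and a check of the few infected participants followed before the change.
3. Reconcile the scale in the Protocol summary, Protocol 4.1.3 and 6.1, and the SAP. This needs wording only.

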### **Other Analyses:**

Other analyses for this study are to determine i) the anti-SARS-CoV-2 antibody titer for individuals at days -1 to 0, 1, 7, 14, and 28 days post-randomization, ii) compare rates and duration of SARS-CoV-2 RNA positivity, and iii) compare levels of SARS-CoV-2 RNA.

Analysis of titers will also primarily be descriptive, comparing the geometric mean titers at days 0, 1, 7, 14, and 90 between the randomized arms. Furthermore, it is of interest to describe the entire distributions of anti-SARS-CoV-2 titers by randomized arms and contrast these distributions. Therefore, we will use quantile regression in order to describe whether there is a shift or change in the titer distribution between randomized arms [Koenker, Quantile Regression, 2005]. Quantile regression does not require the assumption of a parametric or any other type of distribution as it identifies the titer at each percentile. Given that this is a repeated measurement at days 0, 1, 7, 14, and 90 we will account for the correlation within individuals using a cluster bootstrap in order to properly estimate the p-value and 95% confidence intervals.

Analysis of the rate and duration of SARS-CoV-2 PCR positivity between the randomized arms will primarily be descriptive examining proportion positive at days 0, 1, 7, 14, and 28 and then among those who are positive whether individuals lose positivity status at a subsequent visit. To determine the proportion that are positive at each visit, we will do a pooled complementary log-log model in order to describe the cumulative incidence of SARS-CoV-2 PCR positivity over time. The pooled complementary log-log model is a discrete time-to-event-analysis that estimates the log hazard rate at each discrete time point. From this, a cumulative incidence of positivity can be estimated. To determine the duration of positivity, the analysis is complicated by the exact day that an individual becomes positive and the exact day that an individual becomes negative is not known since SARS-CoV-2 PCR positivity will only be acquired at days 0, 1, 7, 14, and 28. However, we can estimate a minimum and maximum amount of time that an individual was positive. For instance if an individual is first positive visit at day 1 and then is positive at day 7 but negative at day 14, then we know that this individual became positive between day 0 and 1 and negative between day 7 and 14. Therefore, the minimum amount of time positive is 7 days (day 8 – day 1) and the maximum is 14 days (day 14 – day 0). Therefore, we can interval censor these individuals. That is, we know that the duration is between 7 and 14 days for this example individual. Across all individuals we can describe the duration of positivity either using a non-parametric approach for time-to-event analysis, but more likely given the sample size, a parametric model. We will assess several parametric distributions aiming for parsimony in the number of parameters being estimated due to the interval censored data which results in increased uncertainty in the model. To determine the best model, we will use Akaike's Information Criterion (AIC) to choose the best model fit. However, if the sample that

becomes positive is small, then we will only be able to describe the observations without a formal statistical model.

We will also describe the distribution of SARS-CoV-2 RNA between randomized arms. This is similar in objective to the comparison of anti-SARS-CoV-2 titers. Therefore, we will use the same approach as above of applying quantile regression.

## **Handling of Missing Data:**

Every effort will be made to minimize missing data in the trial. For participants with missing covariate or outcome data, multiple imputation will be used for sensitivity analyses. Specifically, chained equations (MICE) will be used to predict missing variables but also to generate uncertainty around imputed point estimates.

We will employ recommended strategies to prevent missing data:

- We have developed a data collection schedule that will minimize participant burden and we will follow participants according to the data collection schedule regardless of compliance with the study intervention;
- We will maintain frequent contact with the participants through visit reminder calls, texts, or emails;
- We will provide a 24-hour phone number, which participants can contact for questions and support;
- We will employ rigorous training of clinic staff emphasizing the importance of:
  - Congenial interpersonal relationships between the participants and study staff;
  - Using the consent process to ensure that potential participants understand the commitment that they are making;
  - Addressing concerns if participants are dissatisfied so that the participant will remain in the trial;
  - Attempting to collect as much data as possible even if a participant cannot come to the clinic because of other obligations.

We will collect data on timing and reasons for study dropout by treatment group to present in the CONSORT diagram. If participants who drop out of the study appear to be doing so for reasons related to the study, i.e., not missing completely at random, we will perform sensitivity analyses using methods that have been previously described, such as multiple imputation techniques, best- and worst-case scenarios, and correlates of the drop out event included in the models. There are no standard statistical techniques for dealing with data that are missing not at random (MNAR). We will explore one or more of the sensitivity analyses for MNAR given in the NRC report [National Research Council, 2010]. Baseline characteristics of participants with missing measures will be compared between treatment groups.

